9.4 STATISTICAL ANALYSES

9.4.1 GENERAL APPROACH

All testing described below assumes a significance threshold of $p = 0.05$. Continuous data will be described using means and standard deviations, while categorical data will be described using counts/percentages.

There will be no pre-specified covariates described in this protocol. Data will be assessed for normality and, if deemed necessary, corrective procedures will be applied (e.g., log normalization).

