9. STATISTICAL CONSIDERATIONS

9.1 STATISTICAL HYPOTHESES

- Primary Efficacy hypothesis:
 - Null: There is no difference in changes of alpha frequency power between baseline RSEEG and RSEEG at completion of stimulation between treatment regimens.
 - Alternate: There is a difference in changes of alpha frequency power between baseline RSEEG and RSEEG at completion of stimulation between treatment regimens.
- Secondary Efficacy hypothesis:
 - Null: There is no relationship between the changes in alpha frequency power and changes in Hamilton Depression Rating Scale, 17 item (HDRS17) scores.
 - Alternate: There is a relationship between the changes in alpha frequency power and changes in Hamilton Depression Rating Scale, 17 item (HDRS17) scores.

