9.2 SAMPLE SIZE DETERMINATION

In our recently concluded pilot clinical trial we compared the effects of 10 Hz tACS (therapeutic frequency) against 40 Hz tACS (control frequency) and sham/placebo stimulation. A total of 32 subjects enrolled, 30 completed the 5-day intervention, and 26 completed both a 2 and a 4-week follow-up session. With approximately 9 subjects in each group, a significant reduction was found in alpha oscillation power on the fifth day of stimulation ($p < 0.05$) [6]. Therefore, with a total of 20 subjects (10 in each group), we anticipate we will find a significant difference. Of note, our funding mechanism covers the cost of enrolling 20 participants.

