9.4.2 ANALYSIS OF THE PRIMARY EFFICACY ENDPOINT(S) (EEG)

We will perform spectral analysis of resting state EEG from day 1 of stimulation (baseline), day 5 of stimulation, and the 2-week follow-up visit. We will use a repeated measure ANOVA and/or a general linear mixed-effects model (GLMM) to assess if there is statistically significant interaction between treatment (sham/placebo and 10 Hz tACS) and session (baseline, day 5 of stimulation, 2-week follow-up). In the case of missing data (e.g., missing follow-up visits), analysis using a GLMM will be prioritized, as GLMM takes into account missing data. Spectral analysis will be performed with multi-tapered estimation of the frequency spectrum followed by integration over the classical alpha EEG band (8-12 Hz).

In a separate analysis, we will perform spectral analysis of resting state EEG before and after each separate stimulation session. These analyses will be completed on the modified intention-to-treat dataset. Results from this section will be described in mean decibel (dB) change and presented using spectral images for visualization.

9.4.3 ANALYSIS OF THE SECONDARY ENDPOINT(S)(CORRELATION BETWEEN EEG CHANGES AND SYMPTOMS OF DEPRESSION)

Using the EEG results described in 9.4.2, mean dB change from baseline will be correlated with normalized change in HDRS17 scores.* Correlations will be assessed using Pearson's r and data will be plotted against the best fit line to visualize the results.

*HDRS17 normalization:

$[[\text{HDRS17 score at Visit \#}] - [\text{HDRS17 score at baseline}]] / [\text{HDRS17 score at baseline}]$

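### The primary EEG analysis pre-specifies no adjustment for Day 1 alpha power; adding it is a cheap change that would gain precision unless baseline and day 5 are very highly correlated.

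*Combined protocol and SAP*

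**What the plan says.** Section 9.4.1 (General Approach): "There will be no pre-specified covariates described in this protocol". Section 9.4.2 (primary EEG analysis) plans a repeated-measures ANOVA and/or a mixed model to test the "interaction between treatment (sham/placebo and 10 Hz tACS) and session (baseline, day 5 of stimulation, 2-week follow-up"). Baseline is therefore part of the outcome vector and is not a predictor. The null hypothesis in section 9.1 concerns one interval only: "There is no difference in changes of alpha frequency power between baseline RSEEG and RSEEG at completion of stimulation between treatment regimens".

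Section 6.3 describes 20 randomized codes and no stratification on baseline alpha power. On sample size, section 9.2 says "With approximately 9 subjects in each group, a significant reduction was found in alpha oscillation power on the fifth day of stimulation", and from this that "with a total of 20 subjects (10 in each group), we anticipate we will find a significant difference". It adds "Of note, our funding mechanism covers the cost of enrolling 20 participants". It gives no effect size, standard deviation, power or correlation between visits.

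**The concern.** Day 1 alpha power is recorded on everyone before the first stimulation, so it is available for adjustment at no cost. A change-score comparison fixes the coefficient on baseline at 1. The best coefficient is the regression slope of day 5 on baseline, which equals the correlation rho when the two visits have equal variance. When rho is well below 1, subtracting the whole baseline adds noise. It also pushes the estimate the wrong way when the arms happen to differ at the start, because of regression to the mean.

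With 10 per arm, chance baseline differences are not small and there is little precision to spare. At stake are some power and some interval width on the primary comparison.

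**Working it through.** **The plan's own figure.** N = 20 cannot be reproduced, because no effect size, SD or power is given. A back-calculation is possible only by assuming that the earlier result was a between-group two-sided p of exactly 0.05 with 9 per group. The critical t on 16 df is 2.120, so d = 2.120 x sqrt(2/9) = 1.00. With 10 per arm (18 df) that gives 56% power. If the earlier p was 0.01, d = 1.38 and power is 83%. With 10 per arm, 80% power needs d = 1.32 on the change scale. Two starting points, 56% and 80%, are carried forward.

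**Inputs.** From the documents: 10 per arm and threshold 0.05, taken as two-sided because the alternative in 9.1 is non-directional. Assumed: rho from 0.3 to 0.95, normal data, equal SD at both visits, complete data, and two visits (Day 1 and day 5).

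**What the planned contrast is.** A mixed model fitted to complete simulated three-session data returned treatment-by-session coefficients equal to the between-arm differences in mean change from baseline.

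**Variance of the treatment difference.**
- Change score: (2/n) x 2 x SD^2 x (1 - rho).
- Baseline-adjusted: (2/n) x SD^2 x (1 - rho^2) x [1 + 1/(N - 4)]. The last factor is the cost of estimating the slope, 1 + 1/16 = 1.0625 at N = 20.
- Ratio, adjusted to change score: [(1 + rho)/2] x 1.0625. It equals 1 at rho = 2/1.0625 - 1 = 0.88.

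Simulation used 40,000 trials per setting and compared ANCOVA on 17 df with a t-test on change on 18 df:

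| rho | Ratio, formula | Ratio, simulated | Adjusted power when change score has 56% | Adjusted power when change score has 80% |
|---|---|---|---|---|
| 0.3 | 0.69 | 0.69 | 72% | 92% |
| 0.5 | 0.80 | 0.79 | 66% | 88% |
| 0.7 | 0.90 | 0.91 | 60% | 84% |
| 0.8 | 0.96 | 0.96 | 58% | 81% |
| 0.88 | 1.00 | 1.00 | 56% | 80% |
| 0.9 | 1.01 | 1.01 | 56% | 80% |
| 0.95 | 1.04 | 1.04 | 55% | 79% |

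Type I error is close to 5% for both tests throughout.

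**Worst case.** The adjusted residual variance is the minimum of Var(day 5 - b x baseline) over b, and the change score is the case b = 1. Adjustment therefore cannot cost more than the factor 1.0625, about 6%, plus one error degree of freedom in this two-visit comparison. The cost is greatest when the true slope is near 1. If the day 5 SD is 1.25 times the baseline SD and rho is 0.8 (slope 1.25 x 0.8 = 1), the ratio is 1.06 and power falls from 56% to 54%. If the day 5 SD is 0.8 of baseline and rho is 0.9, the ratio is about 0.65 and power rises from 56% to 75%.

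**Chance imbalance.** The baseline difference d0 between arms has SD sqrt(2/10) = 0.45 SD units and exceeds 0.5 SD in 26% of randomizations. Given d0, the change-score estimate shifts by -(1 - rho) x d0. The simulated slopes on d0 were -0.50, -0.30, -0.20 and -0.10 at rho 0.5, 0.7, 0.8 and 0.9, and zero after adjustment. For example, d0 = 0.5 at rho = 0.5 shifts the estimate by -0.25 SD.

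**The case against.** The strongest reply is that the planned contrast answers the hypothesis in 9.1 directly, is unbiased over randomizations and holds its type I error. On this view the choice is one of efficiency between two valid analyses, and its benefit depends on a correlation the documents do not give. That is right, and it limits the point to an improvement. It does not remove the point, because the possible loss is capped near 6% of variance while the gain at moderate correlations is several times that.

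A second reply also stands in part. The calculation compares two-visit tests, whereas 9.4.2 plans three sessions. Under a repeated-measures ANOVA with compound symmetry, the error has (20 - 2) x (3 - 1) = 36 df, and the 56% becomes about 58.5%. Against that, single-visit adjustment gains only 1-2 points at rho 0.7 and nothing at 0.8, and it is behind from 0.85. The proposed mixed model could pool across sessions too. Neither full model was simulated, so the table shows the order of size and is not a forecast for this trial.

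A reader might infer three stronger things that the documents do not support:
- That the plan forbids covariates. Section 9.4.1 only says that none is pre-specified. Adjustment chosen after seeing the data would nevertheless carry little weight in a trial of 20, so it has to be written in advance.
- That raw baseline imbalance is left in the estimate. The contrast subtracts baseline, so the imbalance is over-corrected.
- That power is certainly lost. At high correlation there is no loss, and adjustment then costs slightly.

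**Conclusion.** The point holds as a cheap improvement to a valid analysis. No adjustment for Day 1 alpha power is pre-specified, and with complete data the baseline-to-day-5 contrast is an unadjusted change score. Adjustment would reduce the variance materially if rho is about 0.7 or lower and slightly at 0.8. It would make no difference near 0.88 and would cost a few percent above that. It would also remove the conditional shift caused by a chance baseline difference. These sizes rest on assumed correlations, equal variances, complete data, a two-visit comparison and, for power, an assumed effect. None of those can be checked from the documents. The documents do not support calling the planned analysis biased or invalid.

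**What to change.** Replace the covariate sentence in 9.4.1 and the model in 9.4.2. Specify a linear mixed model for day 5 and 2-week follow-up alpha power, with treatment, session, treatment-by-session, and Day 1 pre-stimulation alpha power by session as pre-specified fixed effects. Name the treatment difference at day 5 as the primary contrast, which matches the interval in 9.1. Because section 8.1.1 has EEG recorded before and after stimulation each day, the same text should say which day 5 recording is analysed. The change should be written before the allocation codes are opened.

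The cost is wording plus one slope to estimate for each post-baseline session (two in all), with a variance loss of at most about 6% if the slope of day 5 on baseline is close to 1. It needs no new data and no extra participants. The method for small-sample degrees of freedom and the choice of scalp region are separate questions and are not part of this change.

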9.4.2 ANALYSIS OF THE PRIMARY EFFICACY ENDPOINT(S) (EEG)

We will perform spectral analysis of resting state EEG from day 1 of stimulation (baseline), day 5 of stimulation, and the 2-week follow-up visit. We will use a repeated measure ANOVA and/or a general linear mixed-effects model (GLMM) to assess if there is statistically significant interaction between treatment (sham/placebo and 10 Hz tACS) and session (baseline, day 5 of stimulation, 2-week follow-up). In the case of missing data (e.g., missing follow-up visits), analysis using a GLMM will be prioritized, as GLMM takes into account missing data. Spectral analysis will be performed with multi-tapered estimation of the frequency spectrum followed by integration over the classical alpha EEG band (8-12 Hz).

In a separate analysis, we will perform spectral analysis of resting state EEG before and after each separate stimulation session. These analyses will be completed on the modified intention-to-treat dataset. Results from this section will be described in mean decibel (dB) change and presented using spectral images for visualization.

9.4.3 ANALYSIS OF THE SECONDARY ENDPOINT(S)(CORRELATION BETWEEN EEG CHANGES AND SYMPTOMS OF DEPRESSION)

Using the EEG results described in 9.4.2, mean dB change from baseline will be correlated with normalized change in HDRS17 scores.* Correlations will be assessed using Pearson's r and data will be plotted against the best fit line to visualize the results.

*HDRS17 normalization:

$[[\text{HDRS17 score at Visit \#}] - [\text{HDRS17 score at baseline}]] / [\text{HDRS17 score at baseline}]$

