1. PROTOCOL SUMMARY

1.1 SYNOPSIS

Title:	Mechanism of Action of Transcranial Alternating Current Stimulation for the Treatment of Major Depressive Disorder
Study Description:	The purpose of this clinical trial is to investigate the mechanism of action of non-invasive transcranial alternating current stimulation (tACS) in subjects with major depressive disorder (MDD). We will recruit 20 males and females with unipolar, non-psychotic MDD. Eligible subjects will have 5 consecutive 40-minute stimulation sessions. Subjects will be randomly assigned to one of two groups: sham stimulation or 10Hz (alpha) tACS. Participation will include 8 visits, two of them remotely. Participants will give electronic informed consent during the first remote screening sessions. At the initial stimulation session (D1), the electronic consent is printed out and handed to the participant. Eligible subjects will undergo 5 consecutive stimulation sessions with ongoing assessment of suicidality and manic symptoms. Subjects will fill in a questionnaire about stimulation side effects. Neurophysiological measures with high-density EEG will be taken before and after every stimulation session, as well as at the 2-week follow-up visit. Clinical assessments will be performed at baseline (D1), Day 5 of stimulation, and at the follow-up visit using the Hamilton Depression Rating Scale (HDRS-17). Additional assessments of symptomology, quality of life, sleep, and arousal will be completed per the research schedule and are mostly implemented as electronic surveys.
Objectives:	
Primary Objective: To investigate the physiological changes in subjects with MDD over the course of a 5-day, 40-minute stimulation protocol, specifically changes in alpha oscillation power from resting state EEG recordings over the course of the intervention (D1 to D5 of stimulation, to the follow-up visit).
 
Secondary Objectives: To elucidate the relationship between changes in EEG and changes in depressive symptoms, by comparing the changes in clinical assessments (e.g., HDRS) and the change in alpha oscillation power over the course of the intervention (baseline to day 5 of stimulation, to the follow-up visit).

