Endpoints:	
Primary Endpoint: Immediate effects on resting state EEG recordings on each day of stimulation as well as long term effects 2-weeks after stimulation.
 
Secondary Endpoints: Relationship between symptoms of depression per self-report and clinician rated and physiological changes.

Study Population:	We will recruit 20 males and non-pregnant females (age 18-70) with a diagnosis of unipolar, non-psychotic MDD, free of benzodiazepines and anticonvulsant medications. Eligible subjects will have a Hamilton Depression Rating Scale (HDRS-17) > 8 and low suicide risk (determined by scoring less than 3 on the Suicide Item on the HDRS as well as having no active intent as determined by the Columbia Suicide Severity Rating Scale

(C-SSRS). Subjects will be recruited from the Chapel Hill, Durham and Raleigh areas.

Phase:

N/A

Description of

University of North Carolina at Chapel Hill.

Sites/Facilities Enrolling

Participants:

Description of Study

Intervention:

We will use the XCSITE100 stimulator designed by PulvinarNeuro for investigational purposes to deliver either active sham or 10Hz transcranial alternating current stimulation. Active sham treatment will include 20 seconds of ramp in to 40 seconds of 10Hz tACS with a ramp out of 20 seconds for a total of 80 seconds of stimulation. The choice of an active sham is motivated to enhance success of subject blinding by mimicking skin sensations associated with tACS. 10Hz tACS will also have a 20 second ramp in and ramp out with 40-minutes of stimulation for a total of 2440 seconds. Stimulation waveforms are sine-waves with a zero-to-peak amplitude of 1mA. Subjects will stay in a relaxed yet experimentally controlled state by watching a nature movie such as "Reefscape" during stimulation.

2 years

[figure not shown]
Study Duration:

Participant Duration:

[figure not shown]

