2.2 BACKGROUND

MDD has been associated with hypoactivity in the left dorsolateral prefrontal cortex [3], characterized by elevated alpha oscillations [4]. Therefore, targeting and reducing alpha oscillations in the left dorsolateral prefrontal cortex could prove beneficial to patients with MDD. Targeted stimulation modalities, such as transcranial alternating current stimulation (tACS), can directly engage and modulate oscillatory activity. TACS utilizes sine-wave stimulation waveforms that can enhance specific oscillatory activity [5]. The proposed study is a follow-up to a recently concluded trial run by the Carolina Center for Neurostimulation under the direction of [name] [6].

This recently published trial compared the efficacy of 10Hz-tACS (therapeutic frequency, n = 10), 40Hz-tACS (control frequency, n = 10), and sham/placebo stimulation (n = 10). The intervention consisted of 5 consecutive days of 40-minutes of stimulation. Results demonstrated that 2-weeks after completion of the intervention, the 10Hz-tACS group had more subjects responding to treatment (i.e., at least a 50% decrease in depressive symptoms) as measured by the clinician-administered assessments (Montgomery-Asberg Depression Rating Scale, p = 0.026, and Hamilton Depression Rating Scale, p = 0.026). Concurrently, we found that 10Hz-tACS successfully reduced alpha oscillations in the left frontal regions after completion of the stimulation protocol (p < 0.05). While these data demonstrate preliminary efficacy, it is unclear how tACS caused this change, indicating a need to elucidate neurophysiological mechanism of action. Previous work from other groups demonstrate an increase in alpha oscillations following tACS (e.g., [[7]–[9]]), whereas our stimulation paradigm resulted in a decrease in alpha oscillations. Importantly, what is missing is the temporal course of these physiological changes and how they correspond to clinical outcomes. By including high-definition EEG before and after each stimulation, we will be able to delineate the neurophysiological reorganization of alpha oscillations in response to repeated application of tACS.

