8.1.1 PHYSIOLOGICAL CHANGES

1. Resting state EEG (RSEEG) recordings will be completed several times during the study. On every day of the intervention week, subjects will complete an eyes open resting-state EEG (RSEEG) immediately before and after the 40-minutes of stimulation. This measure is used to determine the immediate after-effects of tACS on brain activity, specifically on alpha oscillation power, as well as how consecutive stimulation sessions may affect these after-effects. RSEEG will also be recorded at the follow-up visit to determine the lasting effects of stimulation. An eyes-closed RSEEG will also be collected on Day 1 and at the follow-up visit.

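### The primary null in 9.1 concerns the end of stimulation, but the only primary test in 9.4.2 is a three-session interaction with no day 5 contrast, so it can be significant while that null is true

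*Combined protocol and SAP*

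**What the plan says.** Section 9.1 gives one primary null: "There is no difference in changes of alpha frequency power between baseline RSEEG and RSEEG at completion of stimulation between treatment regimens". Follow-up is not part of it.

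Section 9.2 supports 20 subjects (10 per group) by the earlier trial, where with about 9 per group "a significant reduction was found in alpha oscillation power on the fifth day of stimulation". It gives no effect size, SD or power.

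Section 9.4.2 plans a repeated-measures ANOVA and/or a mixed model to "assess if there is statistically significant interaction between treatment (sham/placebo and 10 Hz tACS) and session (baseline, day 5 of stimulation, 2-week follow-up"). It names no day 5 contrast, no 2-week contrast and no rule for what follows a significant interaction. Section 9.4.1 sets 0.05 for all testing.

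The synopsis (1.1) is wider than 9.1. Its primary objective concerns alpha power "over the course of the intervention (D1 to D5 of stimulation, to the follow-up visit"), and its primary endpoint is "Immediate effects on resting state EEG recordings on each day of stimulation as well as long term effects 2-weeks after stimulation".

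On recordings, 8.1.1 says that on every stimulation day "subjects will complete an eyes open resting-state EEG (RSEEG) immediately before and after the 40-minutes of stimulation". Section 9.4.2 identifies its sessions by day only.

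**The concern.** The interaction null says that the arms do not differ in change at any session. The 9.1 null says that they do not differ in change to the end of stimulation. The first can be false while the second is true, because a difference at the 2-week visit alone is enough. Under the plan as written, a significant primary test could therefore be reported as an end-of-stimulation effect that is not there. A day 5 contrast chosen after the data are seen would have no prespecified status.

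A smaller gap sits beside this. Each stimulation day yields a recording before and one after stimulation, so naming only the day does not fix the quantity compared. This matters in a mechanism trial: 2.2 says that "what is missing is the temporal course of these physiological changes and how they correspond to clinical outcomes", and a post-stimulation recording mixes the acute after-effect with whatever has lasted.

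**Working it through.** **Inputs from the documents.** 10 per arm (9.2); three sessions (9.4.2); threshold 0.05 (9.4.1), taken as two-sided because the alternative in 9.1 is non-directional. Completion of stimulation is read as day 5, which 9.2 supports.

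**Assumptions.** The documents give no EEG effect size, SD or correlation, so the sample size can be neither reproduced nor refuted. Data are taken as complete. Effects *d* are in SDs of the day 1 to day 5 change, and any follow-up effect is on that same scale. The first calculation uses compound symmetry (the same correlation *r* between all sessions), with outcome variance 1, so the SD of change is √(2(1−*r*)).

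**Day 5 change contrast.** A t-test on 18 df has noncentrality *d*/√(2/10). At *d* = 1.0 this is 2.24, giving power 56%. At *d* = 0 it rejects in 5%, whatever happens at follow-up.

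**Interaction.** The test is F on 2 and 2 × (20 − 2) = 36 df. Its noncentrality is (10/2) × Σ(δ − mean δ)²/(1 − *r*), where δ are the three between-arm differences. For an effect at follow-up only, the sum is (2/3) × *d*² × 2(1 − *r*). The noncentrality is then 5 × (2/3) × 2 × *d*² = 6.67*d*², and *r* cancels.

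| Follow-up-only effect (SD of change) | Noncentrality | Interaction significant | Day 5 contrast significant |
|---|---|---|---|
| 0 | 0 | 5% | 5% |
| 0.5 | 1.67 | 18% | 5% |
| 1.0 | 6.67 | 59% | 5% |
| 1.5 | 15.0 | 92% | 5% |

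Simulation (40,000 trials per cell; *r* = 0.5, 0.7, 0.9) agrees with each row to within about one percentage point.

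**Relative power when day 5 differs by 1.0.** An effect at day 5 only, or one that persists in full to follow-up, also gives noncentrality 6.67. The last column requires both tests to be significant.

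| Correlations | Effect at follow-up | Interaction | Day 5 change contrast | Both |
|---|---|---|---|---|
| Compound symmetry | none, or persists | 59–60% | 56–57% | 49% |
| Compound symmetry | halves | 47% | 56% | 44% |
| D1–D5 0.8; both with follow-up 0.5 | none, or persists | 32% | 56% | 26% |

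In the last row the uncorrected repeated-measures F rejects in 6.1% of trials with no effect at any session.

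**The case against.** The strongest reply is that the interaction is the right test and 9.1 is the outlier. The synopsis objective and endpoint both include follow-up, and a three-session test fits them. This stands. The interaction keeps its 5% level for its own null under compound symmetry, so the fault is a mismatch between sections and not an invalid test. It can be repaired from either side.

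Second, the follow-up-only case is the least expected one, since 2.2 and 9.2 place the earlier EEG effect at the end of stimulation. This also stands. The 18–92% describe what a significant result can mean, not how often it would mislead.

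Third, a fitted mixed model would contain a day 5 by treatment term. It would, but the plan does not make that term the test of 9.1.

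Four stronger readings are tempting and not supported:

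- **The interaction is simply weaker, or simply as strong.** Neither holds in general. The order depends on correlations that the documents do not give.
- **The choice between pre- and post-stimulation recordings could reverse the result.** It could decide whether the result is significant, for example if the effect were purely acute, but opposite answers are not shown. The wording of 9.1, with day 1 as baseline in 9.4.2, points to D1 pre-stimulation and D5 post-stimulation. It needs stating, no more.
- **The daily before-and-after analysis inflates false positives.** The synopsis lists daily effects as primary, and 8.1.1 asks "as well as how consecutive stimulation sessions may affect these after-effects". But 9.4.2 names no between-arm daily test and says its results will be described as mean dB change with spectral images. Error rates for five daily tests would concern an analysis that is not planned.
- **Baseline must enter as a covariate.** Section 9.4.1 prespecifies none, and the plain change contrast already tests 9.1.

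**Conclusion.** The concern holds as a mismatch that should be fixed. Following the stated rule, the primary analysis can be positive while the only stated primary null is true. That it can happen follows from the two definitions and needs no assumed value. Its size does: the 18%, 59% and 92% rest on 10 complete subjects per arm, compound symmetry and illustrative effects of 0.5, 1.0 and 1.5 SD confined to follow-up.

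The documents do not support calling the interaction invalid or the trial's expected result misleading. In a 20-subject pilot this is a correction of wording, but one to make before the data are unblinded.

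**What to change.** **Recommended.** In 9.4.2, name the tACS-versus-sham contrast of the day 5 minus day 1 change, from the planned model, as the test of 9.1 at two-sided 0.05. In the same sentence, state the recordings: D1 pre-stimulation and D5 post-stimulation fit 9.1, with D5 pre-stimulation as a supportive check of what has lasted. Report the interaction, and the 2-week contrast with its 95% CI, as supportive.

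This needs no new data and no covariate. Its cost is that an effect present only at 2 weeks no longer makes the primary test positive: at 1.0 SD the chance falls from 59% to 5% under compound symmetry.

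**Alternative.** Widen 9.1 to all three sessions, keep the interaction as primary, and claim an end-of-stimulation effect only if the day 5 contrast is also significant. The recordings still have to be stated. This matches the synopsis but costs day 5 power. At 1.0 SD, the chance of meeting both conditions is 44–49% with the plain change contrast under compound symmetry (about 43–52% if a baseline-adjusted contrast is also considered). It is about 25–27% under the unequal correlations above if the effect is at day 5 only or persists. The recommended contrast has 56% in both settings.

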3. OBJECTIVE AND OUTCOME MEASURES

OBJECTIVES	ENDPOINTS	JUSTIFICATION FOR ENDPOINTS
Primary		
To determine the effect of 10 Hz tACS on brain physiology as measured with electroencephalogram (EEG).	Resting state EEG recordings taken before/after every stimulation session, as well as at a 2-week follow up visit.	The focus is to determine the mechanism of action for five consecutive days of forty-minute tACS stimulation sessions. These endpoints will allow the examination of both immediate and long-term effects of 10 Hz tACS on physiology.
Secondary		
To elucidate the relationship between change in physiology and change in clinical symptoms	Correlations between Hamilton Depression Rating Scale (HDRS), Beck Depression Inventory (BDI) and alpha oscillation power (as measured by resting state EEG recordings).	Previous work indicates that 10 Hz tACS modulates mood and physiology, but there is no clear indication that these changes are related.

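### The daily immediate EEG effect is part of the primary endpoint, but 9.4.2 gives it no comparison with sham and no model across the five sessions

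*Combined protocol and SAP*

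**What the plan says.** The Synopsis (1.1) gives the primary endpoint as "Immediate effects on resting state EEG recordings on each day of stimulation as well as long term effects 2-weeks after stimulation". The table in section 3 agrees: "Resting state EEG recordings taken before/after every stimulation session, as well as at a 2-week follow up visit".

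Section 8.1.1 describes the data: "On every day of the intervention week, subjects will complete an eyes open resting-state EEG (RSEEG) immediately before and after the 40-minutes of stimulation". It says the recordings are meant to show the after-effects of stimulation, "as well as how consecutive stimulation sessions may affect these after-effects". Section 2.2 names the time course of the physiological change as the gap left by earlier work, and gives this as the reason for recording around every session.

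The only between-arm model, in 9.4.2, tests the "interaction between treatment (sham/placebo and 10 Hz tACS) and session (baseline, day 5 of stimulation, 2-week follow-up"). The daily pre/post pairs get one sentence, "In a separate analysis, we will perform spectral analysis of resting state EEG before and after each separate stimulation session", and one on reporting: "Results from this section will be described in mean decibel (dB) change and presented using spectral images for visualization".

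The primary hypothesis in 9.1 concerns the between-arm difference in alpha change from baseline to the end of stimulation. It does not mention the effect of a single session. On thresholds, 9.4.1 says "All testing described below assumes a significance threshold of" p = 0.05 and gives no multiplicity rule.

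**The concern.** The first-named part of the primary endpoint has no analysis that could answer the question asked of it. Two questions are at stake.

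- **Immediate effect.** A pre/post change within the tACS arm mixes any effect of stimulation with that of sitting for 40 minutes watching a nature film (6.1.2). Only a contrast with sham separates them, and none is specified.
- **Build-up.** Whether the after-effect changes over repeated sessions is a treatment by day question. Five separate summaries do not test it.

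The gap also leaves room for choice after the data are seen. An analyst could compare the arms on each day at 0.05 and stress the day that crosses the line, and nothing in 9.4.1 or 9.4.2 would prevent it.

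**Working it through.** **1. Match of endpoint to analysis.**

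| Component | Where stated | Between-arm analysis in 9.4.2 |
|---|---|---|
| Change from baseline to end of stimulation | 9.1 | Treatment by session model, three visits |
| Effect at two weeks | 1.1, 3 | Same model |
| Immediate pre/post effect on each day | 1.1, 3, 8.1.1 | None; mean dB change and images |
| Course of that effect over sessions | 2.2, 8.1.1 | None |

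**2. The plan's own figures.** No power or error rate is given for the daily analysis. Section 9.2 sets 20 participants (10 per group) with no effect size, SD or power, so that figure cannot be reproduced. Working backwards with a two-sided two-sample t-test at 0.05 (18 df), 10 per arm detects a standardised difference of 1.32 with 80% power on any single day.

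**3. Family error if five daily between-arm tests were run.** With independent days, 1 − 0.95^5 = 1 − 0.774 = 22.6%. The five sessions come from the same 20 people, so some positive correlation ρ is likely. The documents give no value, so ρ is an assumption shown as a range. The table uses simulation of five two-sample t-tests, 10 per arm, equal correlation between days.

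**4. One session against the five-day mean.** The variance of a participant's five-day mean, relative to a single day, is (1 + 4ρ)/5. The information lost by using one day is 1 minus this ratio. For power, assume a daily standardised difference d = 0.6 (not in the documents). A single-day test then has 25% power. The five-day mean has the power of a t-test with effect 0.6/√[(1 + 4ρ)/5] on 18 df. At ρ = 0.5 that effect is 0.6/√0.60 = 0.77; at ρ = 0.9 it is 0.6/√0.92 = 0.63.

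| ρ | Family error, five tests | Variance ratio | Information lost by one day | Power, five-day mean | Difference detectable at 80% power, five-day mean |
|---|---|---|---|---|---|
| 0 | 22.6% | 0.20 | 80% | 81% | 0.59 |
| 0.3 | about 21% | 0.44 | 56% | 48% | 0.88 |
| 0.5 | about 19% | 0.60 | 40% | 37% | 1.03 |
| 0.7 | about 15% | 0.76 | 24% | 31% | 1.16 |
| 0.9 | about 10% | 0.92 | 8% | 26% | 1.27 |

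The single test on the five-day mean kept a simulated type I error of 4.8% to 5.1% at every ρ.

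**5. Choice of covariate in a joint model.** Adjusting for each day's pre-stimulation alpha looks natural, but on days 2 to 5 that value is measured after earlier stimulation and can itself be changed by treatment. A simulation took 10 per arm, no immediate effect on any day, tACS lowering pre-stimulation alpha by 0.3 between-participant SD per day, and recording noise of 0.7 SD (all assumptions). With the daily covariate, the build-up term was falsely significant in about 51% of runs and the treatment term in about 17%. With day-1 alpha or no covariate, the figures were about 7% and 1% to 3%.

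**The case against.** The strongest reply is that the daily analysis is descriptive. Section 9.4.2 names no test or p-value for it, and the 0.05 threshold in 9.4.1 applies to tests that are described. A description has no family-wise error rate. That stands. A reader might infer that the plan carries a 23% chance of a false positive; it does not. The figure applies only if someone ran five between-arm tests and counted any one, and it is the value for independent days.

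A reader might also infer that handling one session at a time throws away four-fifths of the data. That is true as a count of sessions. As information it holds only at zero between-day correlation: the loss is 40% at 0.5 and 8% at 0.9.

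It can further be said that sham participants have the same recordings and that 9.4.2 does not rule out comparing the arms. That is correct, but it does not specify a comparison either.

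Finally, the hypothesis in 9.1 has its own joint test in the three-visit model. That too stands: nothing here weakens that test.

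The gap itself survives. A component that the synopsis and section 3 place in the primary endpoint of a sham-controlled trial is left to description alone.

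**Conclusion.** The concern holds as a mismatch between endpoint and analysis. The immediate daily effect and its course over sessions are stated aims, but the plan tests neither against sham. This can be read from the text and needs no outside figure.

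The numbers are conditional. Family error is up to about 23% if five daily between-arm tests were run and any one counted, and at least about 10% over correlations from 0 to 0.9. The gain from one joint test depends on the same unknown correlation: at the assumed d = 0.6, power is 37% against 25% at 0.5, and 26% against 25% at 0.9. The main benefit is therefore one pre-specified comparison with sham and a test of build-up; added power is secondary and may be small.

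The documents do not support reading this as a fault in the three-visit primary test. The change should be made, as a cheap improvement.

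**What to change.** In 9.4.2, replace the separate per-session analysis with one linear mixed model:

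- **Outcome:** post-minus-pre alpha power (dB) for each of the five sessions.
- **Terms:** treatment, day, treatment by day, and a random participant intercept.
- **Immediate effect:** one test, the treatment effect averaged over the five days.
- **Build-up:** the linear treatment by day term.
- **Daily results:** shown by arm with confidence intervals only, without separate tests.
- **Covariate:** none, or day-1 pre-stimulation alpha only. Do not adjust for each day's own pre-stimulation value. If day-1 alpha is used, the line in 9.4.1 that rules out covariates set in advance must be amended.
- **Ranking:** state that this test comes after the test of the 9.1 primary hypothesis.

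All recordings are already planned. The cost is SAP wording and a little more analysis work, and the gain in power over a single-day test will be small if days are highly correlated.
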